## 16.4.2 Neutralizing Anti-drug Antibody

### *Analysis Sets: Immunogenicity analysis set*

Samples with a reportable ADA titer will also be tested in two nAb assays, PD-L1 and TGF- $\beta$ . nAb results are positive or negative in a single assay and only derived when not performed because ADA was negative (see Table 11). Subjects will be characterized into different nAb categories for each assay based on the criteria in Table 12. Treatment boosted is not defined for nAb.

**Table 11** Algorithm for the Derivation of nAb Results

ADA Confirmatory Result	nAb Result	Derived nAb Result
Negative	NA	Negative
NR	NA	NR
NA (screen NR)	NA	NA
NA (screen negative)	NA	Negative
Positive	NR	NR
Positive	Positive	Positive
Positive	Negative	Negative

ADA = antidrug antibody, NA = not applicable, nAb = neutralizing antibody, NR = no result.

**Table 12** Participants Characterized based on nAb Results

Category	Definition	Subject at Risk (Denominator for Incidence)
Never positive	No nAb positive results at any time point	Number of subjects with at least one valid ADA result at any time point
Ever positive	At least one nAb positive result at any time point	Number of subjects with at least one valid ADA result at any time point
Pre-existing	A positive nAb result prior to treatment with bintralusp alfa	Number of subjects with valid ADA baseline result
Treatment emergent	Not nAb positive prior to treatment with bintralusp alfa and with at least one nAb positive post-baseline result	Number of subjects with at least one valid ADA post-baseline result and without nAb positive baseline results (including missing, NR)
Transient positive	If treatment emergent subjects have (a single nAb positive evaluation, or duration between first and last nAb positive result <16 weeks) and last ADA assessment not nAb positive.	Number of subjects with at least one valid ADA post-baseline result and without nAb positive baseline results (including missing, NR)
Persistent positive	If treatment emergent subjects have duration between first and last nAb positive result $\geq$ 16 weeks or a nAb positive evaluation at the last ADA assessment	Number of subjects with at least one valid ADA post-baseline result and without nAb positive baseline results (including missing, NR)

ADA = antidrug antibody, nAb = neutralizing antibody, NR = no result.

The following analysis will be described (the titer summaries will be provided if the titer data is available):

- The frequency and percentage of each nAb category will be tabulated for each assay individually and combined (either assay).
- The nAb titer value by timepoint will be summarized, per assay
- The maximum observed nAb titer per participant per assay will be tabulated. For each discrete titer value, percentages will be calculated using the total number of participants in each nAb status group as the denominator
- The time to first nAb positive response will be summarized, per assay
- The duration of nAb response will be summarized, per assay.

See Section 16.4.1 for the derivation of time to first positive response and duration of response.

The nAb category, titer, maximum titer, time to first nAb positive response and duration of response analyses will also be performed by subgroup:

- Japanese, non Japanese Asian, all Asian, non-Asian.

A listing of nAb results from ever positive participants (in either assay) will be provided with the following: participant ID, age, sex, race, nAb categories status, visit, date of assessment and results of screening and titer values. A further listing will contain: participant ID, age, sex, race, date of first nAb positive result, responder per IRC/investigator, date of response and timing of response related to the date of first nAb positive result. Responders will be defined as participants meeting confirmed CR or PR and non-responders as all other participants.

The following further analyses will also be described as follows:

- Evaluation of potential effect of nAb on bintrafusp alfa safety (see section 15.1.1)
- Evaluation of potential effect of nAb on bintrafusp alfa efficacy
  - for best overall response according to RECIST 1.1 as adjudicated by IRC (see section 14.1.1)
  - for progression-free survival according to RECIST 1.1 as adjudicated by IRC (see section 14.4.2)
  - for duration of confirmed response according to RECIST 1.1 as adjudicated by IRC (see section 14.5.1)
  - for durable confirmed response according to RECIST 1.1 as adjudicated by IRC (see section 14.6.1)
  - for overall survival (see section 14.8.1)
- Evaluation of potential effect of nAb on bintrafusp alfa Pharmacokinetic (see section 16.1.2)

Potential effect of nAb on safety, efficacy and PK will be evaluated on nAb positive status (ever positive in either assay, never positive).

CCI

CCI

## 17

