### Pharmacokinetic nAb Analysis Set (PKNAB)

A subpopulation of the PK Analysis Set restricted to subjects who have in addition at least one valid result of neutralizing anti-drug antibodies (nAb) at any time point.

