### 16.4.1 Antidrug Antibody

The ADA results will be derived for each visit based on the algorithm in Table 9.

**Table 9** Algorithm for the Derivation of ADA Results

Sample Screen Result	Confirmatory	Titer	ADA Result
Negative	NA	NA	Negative
NR	NA	NA	NR
Positive	Negative	NA	Negative
Positive	NR	NA	NR
Positive	Positive	Number	Number
Positive	Positive	NR	Positive-TNR

NR = no result, NA = not applicable, TNR = titer no result.

Note that samples collected during and after the on-treatment period (e.g. safety follow-up) including the ones collected during the re-initiation period will be included in the analysis. Negative, number, or positive-TNR are valid results while number and positive-TNR are considered as positive. Participants will be characterized into different categories based on the criteria in Table 10.

**Table 10** Participants Characterized based on ADA Results

Category	Definition	Participant at Risk (Denominator for Incidence)
Never positive	No positive results at any time point	Number of participants with at least one valid result at any time point
Ever positive	At least one positive result at any time point, including baseline	Number of participants with at least one valid result at any time point
Pre-existing	A positive ADA result prior to treatment with bintrafusp alfa	Number of participants with valid baseline result
Treatment boosted	A positive ADA result prior to treatment with bintrafusp alfa and the titer $\geq 8^*$ baseline titer at least one post-baseline value	Number of participants with valid baseline result and at least one valid post-baseline result
Treatment emergent	Not positive prior to treatment with bintrafusp alfa and with at least one positive post-baseline result	Number of participants with at least one valid post-baseline result and without positive baseline result (including missing, NR)
Transient positive	If treatment emergent participants have - a single positive evaluation or - duration between first and last positive result $<16$ weeks and last assessment not positive	Number of participants with at least one valid post-baseline result and without positive baseline result (including missing, NR)
Persistent positive	If treatment emergent participants have duration between first and last positive result $\geq 16$ weeks or a positive evaluation at the last assessment	Number of participants with at least one valid post-baseline result and without positive baseline result (including missing, NR)

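### SAP Table 12 labels ADA-positive participants with no nAb result as nAb 'never positive'; if any occur, the reported nAb incidence is only a lower bound

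*SAP*

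**What the plan says.** SAP 16.4.2 sets the nAb rules in three steps.

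- **Testing.** "Samples with a reportable ADA titer will also be tested in two nAb assays". Nothing is said about ADA-positive samples without a reportable titer.
- **Sample level (Table 11).** nAb results are "only derived when not performed because ADA was negative". When ADA is confirmed positive and the nAb assay gives no result, the derived value stays NR. No row covers an ADA-positive sample that was not tested for nAb.
- **Participant level (Table 12).** 'Never positive' means "No nAb positive results at any time point". The denominator for both ever and never positive is "Number of subjects with at least one valid ADA result at any time point". No unknown category is defined.

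SAP 16.4.1 says which ADA results are valid: "Negative, number, or positive-TNR are valid results while number and positive-TNR are considered as positive". For ADA itself, the Table 10 denominator for ever and never positive is "Number of participants with at least one valid result at any time point", which there means a valid result of the test being reported.

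The two-level status is then used widely: "Potential effect of nAb on safety, efficacy and PK will be evaluated on nAb positive status (ever positive in either assay, never positive". It enters the AE tables (SAP 15.1.1) and the subgroup analyses of BOR/ORR, PFS, DOR, DRR and OS (SAP 14.1.1, 14.4.2, 14.5.1, 14.6.1, 14.8.1). For PK, SAP 8.2 defines a set (PKNAB) "restricted to subjects who have in addition at least one valid result of neutralizing anti-drug antibodies (nAb) at any time point".

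**The concern.** An nAb result can be positive only on an ADA-positive sample. ADA-negative samples receive a derived negative, so missing nAb results fall only on the participants who could be nAb positive. Table 12 counts those missing results as non-events.

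Two outputs are exposed. One is the nAb incidence, which becomes a lower bound. The other is the 'never positive' reference group in the safety and efficacy comparisons, which may contain undetected nAb positives.

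The SAP's own safeguards do not catch this. The efficacy subgroup sections exclude participants whose subgroup category is missing, but Table 12 assigns these participants a category, so nothing is missing. SAP 9 asks for missing observations to be shown as a separate category unless otherwise stated; Table 12 provides none. SAP 8.2 runs the nAb subgroup analyses only with at least 3 ever-positive participants, so an undercount could also decide whether they are run.

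**Working it through.** **Plan's own figure.** The documents state no ADA incidence, nAb incidence or rate of missing nAb results, so there is nothing to reproduce. The check has two parts: apply the tables literally, then show the effect over assumed inputs.

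**Step 1: literal classification under SAP Tables 9, 11 and 12.**

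| Participant's samples | Table 11 result | Table 12 category | nAb status known? |
|---|---|---|---|
| ADA negative throughout | Negative (derived) | Never positive | Yes |
| ADA positive with titer, nAb negative | Negative | Never positive | Yes |
| ADA positive with titer, nAb positive | Positive | Ever positive | Yes |
| ADA positive with titer, nAb NR only | NR | Never positive | **No** |
| ADA negative at baseline, later ADA positive with nAb NR | Negative, then NR | Never positive | **No** |
| ADA positive without titer, nAb not tested | No row | Never positive | **No** |
| ADA NR only | NR or NA | Not in denominator | Not applicable |

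Three kinds of participant with unknown status are labelled never positive.

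**Step 2: illustration.** N = 141 is the planned sample size (protocol 9.2), and all 141 are taken to have a valid ADA result. The other inputs are assumptions: q = share ADA ever positive, r = share of ADA positives who are truly nAb positive (0.5 below), m = share of ADA positives with no nAb result.

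- ADA positive: A = N × q. Unknown: U = A × m. Observed nAb positive: P = A × (1 − m) × r.
- Table 12 incidence, which is the lower bound: P / N.
- Upper bound, all unknowns positive: (P + U) / N.
- Value if missingness is unrelated to nAb status: q × r.
- Unknowns dropped from the overall denominator: P / (N − U).
- Unknown share of the 'never positive' group: U / (N − P).

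For q = 20% and m = 10%: A = 28.2, U = 2.82 and P = 28.2 × 0.9 × 0.5 = 12.69. Table 12 gives 12.69/141 = 9.0%. The upper bound is 15.51/141 = 11.0%. Dropping unknowns gives 12.69/138.18 = 9.2%. The unknown share of never positive is 2.82/128.31 = 2.2%.

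| q | m | U | Table 12 | Unknowns dropped | Missingness unrelated | Upper bound | Unknown share of never positive |
|---|---|---|---|---|---|---|---|
| 20% | 0% | 0 | 10.0% | 10.0% | 10.0% | 10.0% | 0% |
| 20% | 10% | 2.8 | 9.0% | 9.2% | 10.0% | 11.0% | 2.2% |
| 30% | 20% | 8.5 | 12.0% | 12.8% | 15.0% | 18.0% | 6.8% |
| 40% | 30% | 16.9 | 14.0% | 15.9% | 20.0% | 26.0% | 14.0% |

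The 30% row: P = 42.3 × 0.8 × 0.5 = 16.92 and U = 8.46, giving 16.92/141, 16.92/132.54, 25.38/141 and 8.46/124.08.

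With q between 10% and 40%, r between 25% and 75%, and m between 0% and 30%, the unknown share of the never-positive group runs from 0% to about 15%.

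**Step 3: what the illustration says about the remedy.** Dropping unknowns from the overall denominator recovers 0.2 of the 1.0-point shortfall in the second row and 0.8 of 3.0 points in the third. ADA negatives always have a derived result and stay in, so most of the shortfall remains. Among evaluable ADA positives, the second row gives 12.69/(28.2 − 2.82) = 50.0%, which returns the assumed r when missingness is unrelated to status.

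**The case against.** The strongest reply is that the case may hardly arise and that little depends on it.

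- **Missing results may be rare.** Protocol 9.4.3 says titers of positive samples will be determined and that positive samples may be further evaluated for neutralizing capability. Protocol 8.5 lets PK and ADA samples substitute for each other when quantity is short. Protocol Table 2 samples ADA repeatedly, so a truly nAb-positive participant is missed only if every sample that would have been nAb positive lacks a result. This stands: no document supports a missing rate of 10% to 30%, and the rate could be zero.
- **The analyses are secondary in weight.** The protocol's immunogenicity endpoint is the ADA assay, nAb categorization is optional there, and SAP 8.2 says the study is not powered for subgroups. No hypothesis test uses nAb status. This also stands. While ADA negatives dominate the reference group, dilution of the comparisons would be small.

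Neither reply changes the classification, which follows from the wording of Table 12 whenever such a participant occurs.

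A reader might also infer three stronger points that the documents do not support:

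- *nAb incidence is biased low.* That requires at least one unknown participant who is truly positive, and no rate is given.
- *ADA-positive samples without a titer can never have an nAb result.* The SAP commits to testing titered samples but does not rule out testing others, and the protocol plans to titer all positives.
- *PK summaries are protected by PKNAB and therefore use different nAb groups.* One derived negative from an ADA-negative visit is enough to enter PKNAB, so a participant who is ADA negative at baseline and later ADA positive with nAb NR is 'never positive' there too.

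**Conclusion.** The point holds in conditional form. Table 12 puts ADA-positive participants with no valid nAb result on any ADA-positive sample into 'never positive', although Table 11 keeps their result as NR. This is a stated rule that gives a wrong label, and no other section corrects it for safety or efficacy.

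If any such participants occur, the reported incidence is a lower bound and the reference group for AEs, ORR, PFS, DOR, DRR and OS includes participants of unknown status. The size cannot be taken from the documents. Under the assumed inputs tabulated above, the shortfall against the unrelated-missingness value runs from 0 to 6.0 percentage points (14.0% against 20.0%). It is zero when no nAb result is missing. The primary ORR test does not use nAb status and is unaffected. This is a minor, inexpensive correction.

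**What to change.** - **Table 12, 'never positive'.** Require no positive nAb result and either ADA negative throughout or at least one valid negative nAb result on an ADA-positive sample. Requiring a valid nAb result at every sample would go too far: one NR among several measured negatives would then remove a participant.
- **New category.** Place ADA-positive participants with no valid nAb result on any ADA-positive sample in 'nAb not determined', and leave them out of all ever/never comparisons, including the PKNAB summaries.
- **Incidence.** Report the not-determined count with bounds (all unknowns negative, all unknowns positive), or report nAb incidence among evaluable ADA-positive participants. Removing unknowns from the overall denominator is not sufficient alone.
- **Table 11.** Add a row for ADA-positive samples without a titer.
- **'Either assay' status.** State how it is set when one assay is negative and the other is NR.

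The cost is one extra category and slightly smaller comparison groups. No new samples or tests are needed.

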**18 Appendices**

**18.1.1 Appendix 1: Definition of important protocol deviations**

See document: *ctp-ms200647-0047-iap-v1-appendix-1.docx*

**18.1.2 Appendix 2: Rules for identification of previous or concomitant medications/procedures**

See document: *ctp-ms200647-0047-iap-v1-appendix-2.docx*

**18.1.3 Appendix 3: Definition of NCI-CTCAE grading**

See document: *CTC V5.0 guidance.xlsx*

